12.3.3 Pharmacodynamic Analysis

Continuous pharmacodynamic endpoints with repeated post-baseline assessments (changes from baseline in body weight, whole body adiposity, AVCTE, CAP, ELF, serum hs-CRP, Lp(A), Apo B, LDL, HDL, total cholesterol, triglycerides, FFA, plasma ceramides, HOMA-IR, fasting blood glucose concentrations, glycated albumin concentrations, and HbA_{1c}) will be analyzed for the FAS using a Mixed Model for Repeated Measures (MMRM). This estimand will include available post-baseline response data that occur before discontinuation of treatment. The baseline score will be included as the covariate, and HbA_{1c} stratification, treatment group, visit, and the interaction between treatment group and visit will be included as fixed factors in the MMRM. The difference between each HU6 level versus placebo at each visit will be estimated based on the LSMeans from the MMRM.

12.3.4 Safety Analysis

The safety analysis will be conducted on the FAS. Should there be any subjects that receive a treatment other the randomized treatment, the treatment as received will be used for safety presentations. AEs will be assessed for toxicity grade using NCI CTCAE (Version 5 or higher) and will be coded for summarization using Medical Dictionary for Regulatory Activities (MedDRA[®] Version 10.1 or higher). Concomitant medications will be coded using WHO Drug Dictionary (enhanced) Format C, 15 Aug 2005 or more recent updated version.

Treatment-emergent AEs will be summarized by SOC and preferred term, for each dose group (including placebo). Further summaries by seriousness, severity, and relationship to study drug may be conducted.

Laboratory measures will be summarized by treatment group and time-point both as absolute values and as change from baseline, with descriptive statistics summarizing each group and time point. Similar presentation will be used for vital signs and for ECG interval measurements, and changes from pre-treatment baseline. ECG intervals will be calculated from ECG/continuous ECG recordings at each time point.

A separate statistical analysis plan may be developed for exploratory evaluations of HU6 concentrations and QTcF.

12.3.5 Pharmacokinetic Analysis

Plasma concentration-time data of HU6, DNP and M1 will be displayed in tables and/or graphs. Individual plasma concentration-time data will be pooled, and population pharmacokinetics will be performed using a currently acceptable methods as permitted by the data and based on a prospective analysis plan. PK parameters such as Clearance (CL) and volume of distribution (V) will be determined. In addition, the influence of various covariates (e.g., BMI) of the PK parameters will be examined. Individual PK parameter estimates will be used to calculate summary metrics of exposure including AUC and C_{max} .

Full details will be provided in a Pharmacokinetic Analysis Plan.

12.3.6 Pharmacokinetic/Pharmacodynamic Analyses

PK/PD modeling may be conducted to better define exposure-response and dose determination for future studies, as appropriate.

12.4 Missing, Unused and Spurious Data

No imputation will be applied for missing data. Only non-missing values will be used for analyses.

13 STUDY MANAGEMENT

13.1 Protocol Amendment and Protocol Deviation

13.1.1 Protocol Amendment

Administrative amendments to the protocol will be classed as amendment of typographical errors, clarifications of confusing wording, and other minor modifications including but not limited to name, address, and contact information changes that have no impact on the safety of the subject or the science of the study. Administrative amendments will be submitted to the Institutional Review Board (IRB) for information only. The Sponsor will ensure that acknowledgement is received and filed. Otherwise, an amendment will be classed as a substantial amendment and will be submitted to the appropriate Regulatory Authorities and the IRB for approval.

13.1.2 Protocol Deviations

No deviations from the protocol are anticipated. Requests for deviations must be made in advance with the Sponsor. Should a non-anticipated protocol deviation occur, the Sponsor must be informed as soon as possible. All deviations and the reasons for the deviation will be documented by the Investigator or designated staff. Reporting of protocol deviations to the IRB and in accordance with applicable Regulatory Authority mandates is an Investigator responsibility.

13.1.3 Protocol Waivers

Protocol waivers will not be granted by the Sponsor in this study.

13.2 Ethics and Regulatory Aspects

13.2.1 Ethical Conduct of the Study and Regulatory Guidelines

To ensure the ethical conduct of this clinical study, each Investigator is expected to conduct the study in accordance with the protocol; the United States IND regulations specified under 21 CFR 11, 50, 54, 56, and 312; the ICH Harmonized Tripartite Guideline for Good Clinical Practice (GCP); and the Guidelines of the Declaration of Helsinki. The Investigator will conduct all aspects of the study in accordance with all national, state and local laws of applicable Regulatory Authorities.

The responsibilities of the Sponsor, the Monitor and the Investigator will be as defined in the ICH GCP consolidated guideline, and applicable regulatory requirements in the country where the study takes place. The Investigator is responsible for adhering to the GCP responsibilities of Investigators, for dispensing the study drug in accordance with the approved protocol or a signed amendment, and for its secure storage and safe handling throughout the study.

13.2.2 Institutional Review Board and Regulatory Approval

The study protocol and any amendments will be reviewed by an Independent Review Board. The IRB will review the written subject information sheet and the Informed Consent Form (ICF), their updates (if any), and any written materials given to the subjects. A listing of the membership of the IRB consulted and the name of the committee chair(s) or IRB registry (accreditation) number will be documented within the Investigator File and Trial Master File of the Sponsor.

The Regulatory permission to perform the study must be obtained in accordance with applicable regulatory requirements. All ethics approvals must be obtained, and regulatory obligations met before a subject is exposed to any study-related procedure, including screening tests for eligibility.

13.2.3 Subject Informed Consent

Subjects will be informed about the study both verbally and in writing. Each subject will be provided with a written subject information sheet that has been approved by the IRB and will be given a reasonable time to consider the study and to ask any questions they have regarding the study. The ICF must be in a language that the subject can understand.

Only the Investigator, a medically qualified Sub-investigator or a suitably qualified and trained authorized person may be involved in the informed consent process.

The Investigator or their suitable designee will obtain a freely given, written consent from each subject after an appropriate explanation of the aims, methods, potential hazards, and any other aspects of the study which are relevant to the decision of the subject to participate. The Investigator will explain that the subject is completely free to refuse to enter the study or to withdraw from it at any time, without any consequences for their further care and without the need to justify.

The ICF must be signed and dated by the subject before exposure to any study-related procedure, including screening tests for eligibility. The subject will receive a copy of the written subject information sheet and the ICF.

Each subject will be informed that a Monitor, a Quality Assurance Auditor mandated by the Sponsor, or a Health Authority Inspector, in accordance with applicable regulatory requirements, may review his or her source records and health data. Data protection will be handled in compliance with national and local regulations.

If new safety information becomes available and results in significant changes in the risk to benefit assessment, the written subject information sheet will be revised or updated where necessary. Under these circumstances, all subjects (including those already being treated) should be informed of the new information, given a copy of the revised form and allowed to reevaluate their consent to continue in the study.

13.3 End of Study and Regulatory Notification

The study can be terminated in part or in whole at the discretion of the FDA, an applicable Regulatory Authority or the Sponsor.

At the end of the study, the IRBs and Regulatory Authorities will be notified by the Sponsor according to applicable Regulatory requirements.

13.4 Data Protection and Confidentiality

The confidentiality of records that could identify subjects should be protected, respecting the privacy and confidentiality rules in accordance with applicable regulatory requirement(s).

13.5 Monitoring

The study will be monitored to ensure that the study is conducted and documented properly according to the protocol, GCP, and all applicable regulatory requirements.

On-site visits will be made at appropriate times during the study. Monitors must have direct access to source documentation in order to check the consistency of the data recorded in the CRF.

The Investigator will make available to the Monitor source documents, medical records, and source data necessary to complete CRFs. In addition, the Investigator will work closely with the Monitor and, as needed, provide them appropriate evidence that the conduct of the study is being done in accordance with applicable regulations and GCP guidelines.

13.6 Quality Assurance and Quality Control

The Sponsor or its designee will perform the quality assurance and quality control activities of this study; however, responsibility for the accuracy, completeness, and reliability of the study data presented to the Sponsor lies with the Principal or Qualified Investigator generating the data.

Prior to the study initiation, the Sponsor will explain the protocol, Investigator's Brochure, and CRFs to Investigators. In addition, the Monitor will be available to explain applicable regulations and to answer any questions regarding the conduct of the study.

At its discretion, the Sponsor may conduct audits as part of the implementation of quality assurance to ensure that the study is being conducted in compliance with the protocol, Standard Operating Procedures, GCP, and all applicable regulatory requirements. Audits will be independent of and separate from the routine monitoring and quality control functions.

The study center may also be compelled to an inspection by a Regulatory Authority.

13.7 Source Data

Source data are defined as information in original records and certified copies of original records of clinical findings, observations, data, or other activities in a clinical study necessary for the reconstruction and evaluation of the study.

Source documents are the original data, documents, and records. Examples include hospital records, laboratory reports, clinical and office charts, laboratory notes, memoranda, evaluation checklists, pharmacy dispensing records, recorded data from automated instruments, copies or transcriptions certified after verification as being accurate copies, microfiches, photographic negatives, microfilm or magnetic media, x-rays, other radiographic depictions or displays, subject files, and records kept at the pharmacy, at the laboratories and at medico-technical departments involved in the clinical study. All source documents must be reviewed by the PI and the sponsor (or designee) for compliance with GCP.

Study-specific data sheets may be used to document source information that would not normally be collected and documented in the routine management of the subject. Data sheets used for source

documentation must be verified and signed by the Investigator or a delegated study site team member and must be stored and archived in the subject's clinic records (preferably) or in the Investigator File.

The Investigator will permit study-related monitoring, audit(s), IRB review(s), and regulatory inspection(s), with a direct access to all the required source documents and associated records.

14 DATA AND RECORD KEEPING

14.1 Case Report Forms

All data will be entered in a validated electronic data capture system using single data entry. Standard procedures (including following data review guidelines, manual clinical review based on subject profiles, computerized validation to produce queries, and maintenance of an audit file which includes all database modifications) will be followed to ensure accurate data. Clinical personnel will review all data listings for outliers, data inconsistencies, and spelling errors.

During the course of the study, a study monitor (CRA) will make site visits to review protocol compliance, compare eCRFs against individual subject's medical records, assess drug accountability, and ensure that the study is being conducted according to pertinent regulatory requirements.

Electronic CRF entries will be verified with source documentation. The review of medical records will be performed in a manner to ensure that subject confidentiality is maintained. Checking the eCRFs for completeness, clarity and cross checking with source documents is required to monitor the progress of the study. Direct access to source data is also required for inspections and audits and will be carried out giving due consideration to data protection and medical confidentiality.

14.2 Record Keeping

Study records and source documents need to be preserved for at least 15 years after the completion or discontinuation of/withdrawal from the study or 2 years after the last approval of a marketing application of HU6 in an ICH region, whichever is the longest time period. The sponsor will be notified prior to the planned destruction of any study related source documents.

15 FINANCING AND INSURANCE

Financial aspects of the study are addressed in a separate clinical study agreement.

The Investigator is required to have adequate current insurance to cover claims for negligence and/or malpractice. The Sponsor will provide insurance coverage for the clinical study as required by national regulations.

16 USE OF DATA AND PUBLICATION POLICY

Both the use of data and the publication policy are detailed within the clinical study agreement.

The Investigator should be aware that intellectual property rights (and related matters) generated by the Investigator and others performing the clinical study will be subject to the terms of a clinical study agreement that will be agreed between the Institution and the Sponsor or their designee. With respect to such rights, the Sponsor or their designee will solely own all right and interest in any materials, data and

intellectual property rights developed by the Investigator and others performing the clinical study described in this protocol, subject to the terms of any such agreement. In order to facilitate such ownership, the Investigator will be required to assign all such inventions either to the Institution where the study is conducted or directly to the Sponsor or their designee, as will be set forth in the clinical study agreement. This agreement will not preclude the reporting of any required data to Regulatory Authorities.

18 APPENDICES

Appendix A: AUDIT Questions and Scoring System

Questions	0 Points	1 Point	2 Points	3 Points	4 Points
1. How often do you have a drink containing alcohol?	Never	Monthly or less	2-4 times a month	2-3 times a week	4 or more times a week
2. How many drinks containing alcohol do you have on a typical day when you are drinking?	1 or 2	3 or 4	5 or 6	7-9	10 or more
3. How often do you have 6 or more drinks on 1 occasion?	Never	Less than monthly	Monthly	Weekly	Daily or almost daily
4. How often during the past year have you found that you were not able to stop drinking once you had started?	Never	Less than monthly	Monthly	Weekly	Daily or almost daily
5. How often during the past year have you failed to do what was normally expected of you because of drinking?	Never	Less than monthly	Monthly	Weekly	Daily or almost daily
6. How often during the past year have you needed a first drink in the morning to get yourself	Never	Less than monthly	Monthly	Weekly	Daily or almost daily

Questions	0 Points	1 Point	2 Points	3 Points	4 Points
going after a heavy drinking session?					
7. How often during the past year have you had a feeling of guilt or remorse after drinking?	Never	Less than monthly	Monthly	Weekly	Daily or almost daily
8. How often during the past year have you been unable to remember what happened the night before because you had been drinking?	Never	Less than monthly	Monthly	Weekly	Daily or almost daily
9. Have you or has someone else been injured as a result of your drinking?	No		Yes, but not in the past year		Yes, during the past year
10. Has a relative, friend, or a doctor or other health care worker been concerned about your drinking or suggested you cut down?	No		Yes, but not in the past year		Yes, during the past year

Generic Name	Brand Names (Partial List)	Drug Class	Therapeutic Use	Risk Category	Route
Aclarubicin (Only on Non US Market)	Aclacin, Aclacinomycine, Aclacinon, Aclaplastin, Jaclacin	Anti-cancer	Cancer		injection
Amiodarone	Cordarone, Pacerone, Nexterone	Antiarrhythmic	Arrhythmia		oral, injection
Anagrelide	Agrylin, Xagrid	Phosphodiesterase 3 inhibitor	Thrombocythemia	 	oral
Arsenic trioxide	Trisenox	Anti-cancer	Cancer (leukemia)		injection
Astemizole (Removed from US Market)	Hismanal	Antihistamine	Allergic rhinitis	 	oral
Azithromycin	Zithromax, Zmax	Antibiotic	Bacterial infection	_	oral, injection
Bepridil	Vascor	Antianginal	Angina Pectoris (heart pain)	_	oral
Cesium Chloride	Energy Catalyst	Toxin	Alternative therapy cancer	_	oral, injection
Chloroquine	Aralen	Antimalarial	Malaria		oral
Chlorpromazine	Thorazine, Largactil, Megaphen	Antingvchotic /	Nausea, Schizophrenia, many others	 	oral, injection, suppository
Chlorprothixene (Only on Non US Market)	Truxal	Antipsychotic	Schizophrenia		oral, injection
Cilostazol	Pletal	Phosphodiesterase 3 inhibitor	Intermittent claudication	_	oral
Ciprofloxacin	Cipro, Cipro-XR, Neofloxin	Antibiotic	Bacterial infection	_	oral, injection
Cisapride (Removed from US Market)	Propulsid	GI stimulant	Increase GI motility	_	oral
Citalopram	Celexa, Cipramil	Antidepressant, SSRI	Depression	4	oral
Clarithromycin	Biaxin, Prevpac	Antibiotic	Bacterial infection		oral,

Appendix B: Drugs with Known Risk of Torsade des Pointes

Generic Name	Brand Names (Partial List)	Drug Class	Therapeutic Use	Risk Category	Route
					inhaled
Cocaine	Cocaine	Local anesthetic	Anesthesia (topical)		oral, nasal
Disopyramide	Norpace	Antiarrhythmic	Arrhythmia		oral, injection
Dofetilide	Tikosyn	Antiarrhythmic	Arrhythmia		oral
Domperidone (Only on Non US Market)	Motilium, Motillium, Motinorm Costi, Nomit	Antiemetic	Nausea, vomiting	 	oral, injection, suppository
Donepezil	Aricept	Cholinesterase inhibitor	Dementia (Alzheimer's Disease)	 	oral
Dronedarone	Multaq	Antiarrhythmic	Arrhythmia	 	oral
Droperidol	Inapsine, Droleptan, Dridol, Xomolix	Antipsychotic / Antiemetic	Anesthesia (adjunct), nausea	_	injection
Erythromycin	E.E.S., Robimycin, EMycin, Erymax, Ery- Tab, Eryc Ranbaxy, Erypar, Eryped, Erythrocin Stearate Filmtab, Erythrocot, E- Base, Erythroped, Ilosone, MY-E, Pediamycin, Abboticin, Abboticin-ES, Erycin, PCE Dispertab, Stiemycine, Acnasol, Tiloryth	Antibiotic	Bacterial infection, increase GImotility	A 🏖	oral, injection
Escitalopram	Cipralex, Lexapro, Nexito, Anxiset-E, Exodus, Esto, Seroplex, Elicea, Lexamil, Lexam, Entact, Losita, Reposil, Animaxen, Esitalo, Lexamil	Antidepressant, SSRI	Depression (major), anxietydisorders	A 🕹	oral
Flecainide	Tambocor, Almarytm, Apocard, Ecrinal, Flécaine	Antiarrhythmic	Arrhythmia	 	oral
Fluconazole	Diflucan, Trican	Antifungal	Fungal infection	 	oral, injection
Gatifloxacin (Removed from US Market)	Tequin	Antibiotic	Bacterial infection	_	oral, injection
Grepafloxacin (Removed from US Market)	Raxar	Antibiotic	Bacterial infection	_	oral
Halofantrine (Only on Non US Market)	Halfan	Antimalarial	Malaria		oral

Generic Name	Brand Names (Partial List)	Drug Class	Therapeutic Use	Risk Category	Route
Haloperidol	Haldol, Aloperidin, Bioperidolo, Brotopon, Dozic, Duraperidol, Einalon S, Eukystol, Halosten, Keselan, Linton, Peluces, Serenace, Serenase, Sigaperidol	Antipsychotic	Schizophrenia, agitation	A 🕹	oral, injection
Hydroquinidine (Dihydroquinidine) (Only on Non US Market)	Serecor	Antiarrhythmic	Arrhythmia	A &	oral
Hydroxychloroquine	Plaquenil, Quineprox	Antimalarial, Anti- inflammatory	Malaria, SLE, rheumatoid arthritis	 	oral
lbogaine (Only on Non US Market)		Psychedelic	Narcotic addiction, unproven	 	oral
lbutilide	Corvert	Antiarrhythmic	Arrhythmia	 	injection
Levofloxacin	Levaquin, Tavanic	Antibiotic	Bacterial infection	 	oral, injection
Levomepromazine (Methotrimeprazine) (Only on Non US Market)	Nosinan, Nozinan, Levoprome	Antipsychotic	Schizophrenia	A 🕹	oral, injection
Levomethadyl acetate (Removed from US Market)	Orlaam	Opioid agonist	Narcotic dependence	A 😂	oral
Levosulpiride (Only on Non US Market)	Lesuride, Levazeo, Enliva	Antipsychotic	Schizophrenia	_	oral, injection
Meglumine antimoniate (Only on Non US Market)	Glucantime	Antiparasitic	Leishmaniasis	A 🕹	injection
Mesoridazine (Removed from US Market)	Serentil	Antipsychotic	Schizophrenia	^ &	oral
Methadone	Dolophine, Symoron, Amidone, Methadose, Physeptone, Heptadon	Opioid agonist	Narcotic dependence, pain		oral, injection
Moxifloxacin	Avelox, Avalox, Avelon	Antibiotic	Bacterial infection	 	oral, injection
Nifekalant	Shinbit	Antiarrhythmic	Arrhythmia	A 🔛	injection

Generic Name	Brand Names (Partial List)	Drug Class	Therapeutic Use	Risk Category	Route
(Only on Non US Market)					
Ondansetron	Zofran, Anset, Ondemet, Zuplenz, Emetron, Ondavell, Emeset, Ondisolv, Setronax	Antiemetic	Nausea, vomiting		oral, injection, suppository
Oxaliplatin	Eloxatin	Anti-cancer	Cancer		injection
Papaverine HCl (Intra- coronary)		Vasodilator, Coronary	Diagnostic adjunct	 	injection
Pentamidine	Pentam	Antifungal	Fungal infection (Pneumocystis pneumonia)		injection, inhaled
Pimozide	Orap	Antipsychotic	Tourette's Disorder	A 🍪	oral
Probucol (Removed from US Market)	Lorelco	Antilipemic	Hypercholesterolemia	. &	oral
Procainamide	Pronestyl, Procan	Antiarrhythmic	Arrhythmia	 	injection
Propofol	Diprivan, Propoven	Anesthetic, general	Anesthesia	▲ 🍪	injection
Quinidine	Quinaglute, Duraquin, Quinact, Quinidex, Cin-Quin, Quinora	Antiarrhythmic	Arrhythmia	▲ 🍪	oral, injection
Roxithromycin (Only on Non US Market)	Rulide, Xthrocin, Roxl-150, Roxo, Surlid, Rulide, Biaxsig, Roxar, Roximycinv, Roxomycin, Rulid, Tirabicin, Coroxin	Antibiotic	Bacterial infection	 	oral
Sertindole (Only on Non US Market)	Serdolect, Serlect	Antipsychotic, atypical	Schizophrenia, anxiety	 	oral
Sevoflurane	Ultane, Sojourn	Anesthetic, general	Anesthesia	 	inhaled
Sotalol	Betapace, Sotalex, Sotacor	Antiarrhythmic	Arrhythmia	A 🍪	oral
Sparfloxacin (Removed from US Market)	Zagam	Antibiotic	Bacterial infection	.	oral
Sulpiride (Only on Non US Market)	Dogmatil, Dolmatil, Eglonyl, Espiride, Modal, Sulpor	Antipsychotic, atypical	Schizophrenia		oral, inhaled

Generic Name	Brand Names (Partial List)	Drug Class	Therapeutic Use	Risk Category	Route
Sultopride (Only on Non US Market)	Barnetil, Barnotil, Topral	Antipsychotic, atypical	Schizophrenia	A 🏼	oral, injection
Terfenadine (Removed from US Market)	Seldane	Antihistamine	Allergic rhinitis	A &	oral
Terlipressin (Only on Non US Market)	Teripress, Glypressin, Terlipin, Remestyp, Tresil, Teriss	Vasoconstrictor	Septic shock	A 🕹	injection
Terodiline (Only on Non US Market)	Micturin, Mictrol	Muscle relaxant	Bladder spasm	A 🕹	oral
Thioridazine	Mellaril, Novoridazine, Thioril	Antipsychotic	Schizophrenia	 	oral
Vandetanib	Caprelsa	Anti-cancer	Cancer (thyroid)		oral

Known Risk of TdP - Substantial evidence supports the conclusion that these drugs prolong the QT interval AND are clearly associated with a risk of TdP, even when taken as directed in official labeling.

Drugs to Avoid in Congenital Long QT - Substantial evidence supports the conclusion that these drugs pose a risk of TdP for patients with congenital long QT. Drugs on this list include those in the above three risk categories and other drugs that do not prolong the QT interval per se but they have a theoretical risk of causing arrhythmia that is based on their known stimulant actions on the heart.

Last revision: 17Dec2020 https://crediblemeds.org/

Appendix C: Algorithm for Monitoring and Management of Possible Hepatocellular DILI in Phase 2 or 3 NASH Clinical Studies

Treatment-emergentALTNormal/near normal baseline ^a :ALT \geq 5× ULNElevated baseline ^a :ALT \geq 3× baseline or \geq 300 U/L(whichever occurs first)	Treatment-emergent Total Bilirubin Normal Patients with Gilbert's syndrome: No change in baseline TBL	Liver-related Symptoms None	Action ^b Repeat ALT, AST, ALP, TBL, in 2-5 days. Follow- up for symptoms. Initiate evaluation for other etiologies of abnormal liver tests.
Normal/near normal baseline ^a : ALT ≥3× ULN Elevated baseline ^a : ALT ≥2× baseline or ≥300 U/L (whichever occurs first)	Normal Patients with Gilbert's syndrome: No change in baseline TBL	Severe fatigue, nausea, vomiting, right upper quadrant pain	Repeat ALT, AST, ALP, TBL, in 2-5 days. Follow- up for symptoms. Initiate evaluation for other etiologies of abnormal liver tests.
Normal/near normal baseline ^a : ALT ≥8× ULN Elevated baseline ^a : ALT ≥5× baseline or ≥500 U/L (whichever occurs first)	Normal Patients with Gilbert's syndrome: No change in baseline TBL	None	Interrupt study drug. Initiate close monitoring and workup for competing etiologies. Study drug can be restarted only if another etiology is identified and liver enzymes return to baseline.
Normal/near normal baseline ^a : ALT \geq 3 ULN Elevated baseline ^a : ALT \geq 2× baseline or \geq 300 U/L (whichever occurs first)	TBL ≥2× ULN Patients with Gilbert's syndrome: Doubling of direct bilirubin or increased INR to >1.5	None d	Interrupt study drug. Initiate close monitoring and workup for competing etiologies. Study drug can be restarted only if another etiology is identified, and liver enzymes return to baseline.
Normal/near normal baseline ^a :" ALT ≥5 ULN Elevated baseline ^a : ALT ≥3× baseline or ≥300 U/L (whichever occurs first)	Normal or elevated	Severe fatigue, nausea, vomiting, right upper quadrant pain	Interrupt study drug. Initiate close monitoring and workup for competing etiologies. Study drug can be restarted only if another etiology is identified, and liver enzymes return to baseline.

ALP, alkaline phosphatase; ALT, alanine aminotransferase; AST, aspartate aminotransferase; DILI, drug-induced liver injury; INR, international normalized ratio; TBL, total bilirubin, ULN, upper limit of normal.

a. Baseline ALT is derived from an average of two pre-treatment ALT measurements at least 2 weeks apart. Elevated baseline is defined as ALT \geq 1.5×ULN. In patients with a sizable stable decrease in ALT (>50% of the baseline value) during treatment, a new baseline, corresponding to the ALT nadir, should be established on an individual basis for subsequent determination of a DILI signal.

b. The actions of close observation, monitoring, and drug interruption often overlap. Occasionally, workup is initiated after drug interruption.

For further details, please see full Consensus and Recommendation list in Regev A et al., 2019.

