- 6. Increased liver function tests will be evaluated in accordance with the Consensus guidelines for best practices for the detection, assessment, and management of suspected acute drug-induced liver injury (DILI) during clinical trial in patients with nonalcoholic steatohepatitis which are applicable to the subjects being enrolled in this trial (Regev et al., 2018). Please see Appendix C for a table from that Consensus that shows the algorithm for monitoring and managing of hepatocellular DILI in phase 2-3 NASH clinical trials in patients with normal or elevated baseline ALT, as well as the listing of the Consensus and Recommendations.
- 7. Administrative reason (e.g., termination of the clinical study by a Regulatory Agency or the Sponsor).
- 8. Lost to follow-up.
- 9. Pregnancy.

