11.7.3 Adverse Event Follow-up

Adverse events requiring therapy must be treated with recognized standards of medical care to protect the health and well-being of the subject.

Any subject who has any AE (whether serious or non-serious) or clinically significant (in the Investigator's opinion) abnormal laboratory test values will be evaluated by the Investigator or a monitoring physician, and will be treated and followed up until the symptoms or values return to normal or acceptable levels, as judged by the Investigator and the Sponsor.

Adverse events that are unresolved at end of study or upon early withdrawal will be tracked at least weekly by site staff until resolution, for 30 days, or until the subject is lost to follow-up (defined as failure to respond to three phone messages left on separate days and one certified letter requesting follow-up).

Subjects will be instructed to inform site staff of any AEs occurring during the 30-day period after discharge or early withdrawal.

Any follow-up information available at the time of the subject's end of study will be included in the clinical study report.

Any SAE that is unexpected and related to the study drug occurring after the end of study should be forwarded to the Sponsor. These cases will be handled and submitted as expedited reports but will not be included in the clinical study report.

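### Appendix C prints no action for bilirubin above normal but below 2× ULN in three ALT/symptom situations where it does act at normal bilirubin

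*Protocol*

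**What the plan says.** Section 7.4, item 6, sends raised liver tests to an external guideline: "Increased liver function tests will be evaluated in accordance with the Consensus guidelines for best practices". It then points to Appendix C, a table taken from that guideline. Appendix C holds the only numeric liver interruption thresholds printed in the protocol.

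The table has five rows, each combining an ALT threshold, a bilirubin condition, a symptom condition and an action. I number them in printed order.

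- Rows 1 to 3 need normal bilirubin. The column header and the row 1 cell run together in the text as "Treatment-emergent Total Bilirubin Normal Patients with Gilbert's syndrome: No change in baseline TBL"; rows 2 and 3 carry the same cell.
- Row 3 is the symptom-free interruption row: "ALT ≥8× ULN Elevated baseline ^a : ALT ≥5× baseline or ≥500 U/L (whichever occurs first").
- Row 4 interrupts at a lower ALT, but its bilirubin cell is "TBL ≥2× ULN Patients with Gilbert's syndrome: Doubling of direct bilirubin or increased INR to >1.5".
- Row 5 alone accepts normal or elevated bilirubin. It needs severe symptoms and ALT ≥5× ULN or, with an elevated baseline, "ALT ≥3× baseline or ≥300 U/L" (whichever comes first).

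The interruption rows carry a restart condition, worded in row 3 as "Study drug can be restarted only if another etiology is identified and liver enzymes return to baseline".

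Outside the table, Section 11.7.3 says that a subject with an AE or a clinically significant abnormal value "will be treated and followed up until the symptoms or values return to normal or acceptable levels".

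**The concern.** Bilirubin rising together with ALT is a worse liver picture than the same ALT with normal bilirubin. A stopping table should therefore never give a lesser action as bilirubin rises. Read row by row, this one does: between the upper limit of normal and 2× ULN, rows 1 to 3 stop applying and row 4 has not yet started. The contrast with row 5, which says explicitly that bilirubin may be normal or elevated, suggests that *Normal* in rows 1 to 3 is a real condition.

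At stake is uniform handling across up to five centers. In the affected cells the protocol prints no interruption threshold, no 2-5 day retest and no restart condition.

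The band can be reached. Any subject's bilirubin may rise into it on treatment. In addition, exclusion 33 admits some subjects with total bilirubin already above ULN: those with Gilbert's syndrome, and others judged to show normal variability with the Medical Monitor's approval.

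**Working it through.** No stated figure needs reproducing. The check is to list which row fires in each combination.

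**Inputs (Appendix C).** The elevated-baseline threshold is the lower of the two values given, since the table takes whichever is reached first. Footnote a defines an elevated baseline as ALT ≥1.5× ULN.

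| Row | ALT, near-normal baseline | ALT, elevated baseline | Bilirubin | Symptoms | Action |
|---|---|---|---|---|---|
| 1 | ≥5× ULN | ≥3× baseline or ≥300 U/L | normal | none | repeat in 2-5 days |
| 2 | ≥3× ULN | "ALT ≥2× baseline or ≥300 U/L" | normal | severe | repeat in 2-5 days |
| 3 | ≥8× ULN | ≥5× baseline or ≥500 U/L | normal | none | interrupt |
| 4 | ≥3× ULN | ≥2× baseline or ≥300 U/L | ≥2× ULN | unclear in the text | interrupt |
| 5 | ≥5× ULN | ≥3× baseline or ≥300 U/L | normal or elevated | severe | interrupt |

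**Near-normal baseline, by bilirubin.**

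| Symptoms | ALT (× ULN) | Bilirubin normal | Above normal, <2× ULN |
|---|---|---|---|
| none | 3 to <5 | no row | no row |
| none | 5 to <8 | row 1: repeat | **no row** |
| none | ≥8 | row 3: interrupt | **no row** |
| severe | 3 to <5 | row 2: repeat | **no row** |
| severe | ≥5 | row 5: interrupt | row 5: interrupt |

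Three cells lose their action when bilirubin rises above normal. Symptom-free ALT of 3 to <5× ULN is not counted: it has no row at normal bilirubin either, so it may be intended as no action.

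**Elevated baseline.** The same three bands run:

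1. no symptoms, from min(5× baseline, 500) upward;
2. no symptoms, from min(3× baseline, 300) to below min(5× baseline, 500);
3. severe symptoms, from min(2× baseline, 300) to below min(3× baseline, 300).

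Band 3 is empty once 2 × baseline ≥ 300, that is, baseline ≥ 300 / 2 = 150 U/L.

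**In U/L.** The documents give no ULN for ALT, so 40 U/L is assumed. The assumption sets the U/L values in the first line below and decides who counts as elevated (1.5 × 40 = 60 U/L). The bands themselves do not depend on it. For a near-normal baseline, 3 × 40 = 120, 5 × 40 = 200 and 8 × 40 = 320. For a baseline of 120, min(360, 300) = 300, min(600, 500) = 500 and 2 × 120 = 240.

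| Baseline ALT (U/L) | Interrupt becomes no row (no symptoms) | Repeat becomes no row (no symptoms) | Repeat becomes no row (severe symptoms) |
|---|---|---|---|
| 30 | 320 and above | 200-319 | 120-199 |
| 60 | 300 and above | 180-299 | 120-179 |
| 80 | 400 and above | 240-399 | 160-239 |
| 120 | 500 and above | 300-499 | 240-299 |
| 150, 160, 200 | 500 and above | 300-499 | none |

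The baselines run up to 5 × 40 = 200 U/L, the highest screening ALT that exclusion 32 admits under this ULN. Stepping through ALT 40-800 U/L in steps of 1 gave these ranges.

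**Gilbert's syndrome.** Rows 1 to 3 need an unchanged baseline bilirubin. Row 4 needs a doubling of direct bilirubin or INR >1.5. A rise in total bilirubin without either falls in the same gap.

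**The case against.** The strongest reply is that Appendix C is an extract, not the whole rule. Section 7.4 makes evaluation of raised liver tests under the full consensus mandatory, and the last line of the appendix refers back to it. That source is not available here and may cover the band. This stands, and it limits the point to what is printed.

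The general safety text is also substantial. Section 11.7.3 requires evaluation and follow-up. Section 11.7.1 counts stopping drug and closer follow-up as active management of a laboratory abnormality. Section 11.7.2.4 lists temporary interruption as an available action. Section 7.4 allows withdrawal for safety. Footnote b says that observation, monitoring and interruption often overlap. An investigator who sees interruption in row 3 at normal bilirubin and in row 4 at 2× ULN would probably interrupt in between. All this makes inaction unlikely, but none of it states a threshold, a retest interval or a restart condition for the three cells.

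Three stronger readings are tempting and are not supported:

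- *Dosing must continue in these cells.* A missing row is not an instruction to continue, and evaluation is required in any case.
- *A case found at Day 28 would go unchecked until the next scheduled chemistry at Day 61, 61 − 28 = 33 days later.* This assumes no unscheduled retest. Section 8 gives unscheduled safety procedures precedence, and Section 11.5 allows extra laboratory tests when an AE is assessed.
- *Row 4 also fails for symptomatic subjects.* Its symptom cell reads as none followed by a stray d, and no footnote d is visible, so the text may be garbled. The three gaps above are the same whichever way that cell is read.

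**Conclusion.** The gap is real in the printed table. With total bilirubin above normal but below 2× ULN, the printed action falls from interrupt to nothing in one situation and from repeat to nothing in two. The third situation disappears for baselines of 150 U/L or more.

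The consequence is limited. Evaluation and follow-up remain mandatory. What is left to judgment is when to stop drug, how soon to retest and when restart is allowed. The documents give no event rate; such events are expected to be rare, and no efficacy result is affected. I rate it minor, with moderate confidence.

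The conclusion assumes that *Normal* means not above the upper limit (or, in Gilbert's syndrome, unchanged from baseline) and that the unseen consensus is not part of the printed rule. For other subjects enrolled above ULN, the table does not say whether a pre-existing elevation counts as treatment-emergent.

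**What to change.** Make two changes to Appendix C:

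1. In row 3, change the bilirubin cell to *Normal or elevated*, the wording row 5 already uses. Overlap with row 4 does no harm, since both rows interrupt.
2. Add one sentence under the table: *Bilirubin above normal (or, in Gilbert's syndrome, above baseline) never lowers the action; at least the action for the same ALT and symptoms at normal bilirubin applies, and the most restrictive matching row governs.*

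The first change closes the symptom-free ALT ≥8× ULN cell and brings the restart condition with it. The second closes the two repeat-test cells and the Gilbert's case. Because it says *at least*, the 2-5 day repeat is a minimum for a severely symptomatic subject with raised bilirubin, and the investigator stays free to interrupt.

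The cost is one amended appendix table and a memo to sites, plus a few more mandated interruptions and unscheduled repeat panels. No scheduled tests or subjects are added. The sponsor should check the wording against the full consensus before issuing it.
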